Safety and Effectiveness Evaluation of Eximo's B-LaserTM Atherectomy Device, in Subjects Affected with PAD – a Clinical Study Protocol Synopsis

Date: 20 Nov 2016

PRODUCT: Eximo Medical B-Laser™ for PAD

Page 1 of 3

Document number: EX-PAD-01

Revision: 05

Study Title:	Safety & effectiveness evaluation of Eximo's B-Laser™ Atherectomy Device, in subjects affected wit						
	Peripheral Arterial Disease (PAD), Study Protocol ID: EX-PAD-01 [NCT02556255]						
Study Design:	Prospective, single-arm, multi-center, international, open-label, non-randomized clinical study.						
Objective:	To assess the safety and efficacy of the use of Eximo's B-Laser™ catheter in subjects affected with PAD in lower extremity arteries.						
Subject	Men and Women with symptomatic occlusive PAD in lower extremity arteries that are scheduled for						
Population:	PAD endovascular intervention and are eligible according to protocol inclusion / exclusion criteria.						
Study	Primary Endpoint - Safety:						
Endpoints:	30 day Freedom from the following Major Adverse Events (MAE):						
	Need for emergency surgical revascularization of the target limb						
	 Unplanned target limb amputation above the ankle 						
	Clinically driven target lesion revascularization (TLR)						
	o Cardiovascular related deaths						
	Perioperative (until discharge) freedom from the following Device/Procedure ¹ Related Adverse						
	Events (AE):						
	Clinically Significant target vessel's Perforations requiring intervention						
	 Clinically Significant target vessel's Dissections requiring intervention 						
	 Clinically Significant target vessel's distal embolization or in-situ thrombus requiring intervention 						
	Clinically significant target vessel's Pseudo-aneurysm requiring intervention						
	Primary Endpoint – Effectiveness - Technical Success:						
	 Ability of the B-Laser™ to cross the target lesion stenosis over the wire while the stenotic flow diameter is smaller than the B-Laser™ diameter. 						
	Secondary Endpoint - Safety:						
	Perioperative (until discharge) freedom from the following Device/Procedure ¹ Related Adverse						
	Events:						
	o Emboli, defined as a new occlusion of any visualized runoff vessel which cannot be reversed with						
	an intravascular vasodilator						
	Flow limitation dissection						
	30 day freedom from the following Device/Procedure ¹ Related Adverse Events:						
	Clinically Significant target vessel's Dissections requiring intervention						
	 Clinically Significant target vessel distal embolization or in-situ thrombus requiring intervention 						
	Clinically Significant target vessel's Pseudo-aneurysm requiring intervention						
	Secondary Endpoints – Effectiveness:						
	 The ability of the B-Laser[™] device to achieve a post-intervention residual diameter stenosis of 						
	<30% with adjunctive therapy as assessed by fluoroscopic angiography in cases where adjunctive						
	therapy is medically applicable						
	o Improved Ankle-Brachial Index (ABI) at 30 days, 6 months and 12 months post B-Laser™ device						
	procedure compared to baseline.						
	o Improved Rutherford Classification at 30 days, 6 months and 12 months post B-Laser™ device						
	procedure compared to baseline.						
	o Improved Grade of Walking Impairment Questionnaire (WIQ) at 30 days, 6 month and 12 months						
	post B-Laser [™] device procedure compared to baseline.						

.

¹ Device/Procedure-related AE refers only to B-Laser™ atherectomy procedure and not the entire index procedure

Safety and Effectiveness Evaluation of Eximo's B-LaserTM Atherectomy Device, in Subjects Affected with PAD – a Clinical Study Protocol Synopsis

Date: 20 Nov 2016

PRODUCT: Eximo Medical B-Laser™ for PAD

Page 2 of 3

Document number: EX-PAD-01

Revision: 05

Inclusion Criteria

- 1. Subject is \geq 18 years old.
- 2. Subject is a candidate for endovascular intervention for PAD in the lower extremities.
- 3. Documented symptomatic atherosclerotic PAD Rutherford Classification 2-4.
- 4. Subject has infrainguinal target lesion(s) with any type of stenosis (naïve or recurrent) estimated to be ≥70% based on CT angiogram or other imaging modality.
- 5. At least one patent tibial run-off vessel at baseline.
- 6. Subject is capable and willing to comply with the scheduled follow up.
- 7. Subject is able and willing to sign a written informed consent form (ICF).

Intraoperative inclusion criteria (by fluoroscopy angiogram):

- Reference vessel lumen diameter proximal to target lesion is ≥150% of the outer diameter of the B-Laser™ to be used.
- 2. Target lesion has been crossed with a guidewire within the true lumen.
- 3. Target lesion has a stenosis estimated to be ≥70%.

Exclusion Criteria

- 1. Target lesion is in a vessel graft or synthetic graft.
- 2. Target lesion length >25 cm.
- 3. Endovascular or surgical procedure performed less than or equal to 30 days prior to index procedure OR Planned endovascular or surgical procedure 30 days post index procedure.
- 4. Intent to use other atherectomy device in the same procedure.
- 5. Flow limiting dissection proximal to, distal to or in the target lesion.
- 6. Evidence or history of intracranial or gastrointestinal bleeding, intracranial aneurysm, myocardial infarction or stroke within the past 2 months.
- 7. Evidence or history of aneurysm in the target vessel within the past 2 months.
- 8. History of bleeding diathesis, coagulopathy or inability to accept blood transfusions.
- 9. History of heparin-induced thrombocytopenia (HIT).
- 10. Significant acute or chronic kidney disease with a creatinine level >2.5 mg/dl, and/or requiring dialysis.
- 11. Any thrombolytic therapy within 2 weeks of the index procedure.
- 12. History of severe trauma, fracture, major surgery or biopsy of a parenchymal organ within the past 14 days.
- 13. Known allergy to contrast agents or medications used to perform endovascular intervention that cannot be adequately pre-treated.
- 14. Subjects in whom anti-platelet, anticoagulant, or thrombolytic therapy is contraindicated.
- 15. Serious illness that may affect subject compliance to protocol and at a minimum the 30-day follow-up.
- 16. Participating in other clinical study that involves any kind of intervention, including pharmaceutical.
- 17. Issue that in the judgment of the investigator, may affect the results of the study.
- 18. Subject is pregnant or planning to become pregnant during the study period.

Intraoperative exclusion criteria (by fluoroscopy angiogram):

- 1. Total occlusion of the Target lesion that cannot be crossed in the true lumen by 0.014" GW.
- 2. Target lesion length >25 cm.
- 3. Reference vessel lumen diameter proximal to target lesion <150% of B-Laser™ diameter.
- 4. Any clinical and/or angiographic complication attributed to the use of another device prior to study procedure.
- 5. Flow limiting dissection proximal, distal or in the target lesion.

Safety and Effectiveness Evaluation of Eximo's B-LaserTM Atherectomy Device, in Subjects Affected with PAD – a Clinical Study Protocol Synopsis

Date: 20 Nov 2016

PRODUCT: Eximo Medical B-Laser™ for PAD

Page 3 of 3

Document number: EX-PAD-01

Revision: 05

Study Duration:	30 days post procedure for the primary endpoint and up to 12 months for the secondary endpoints for each subject. Therefore, total study expected duration is 15.5 months (3.5 m + 12 m follow-up).
Number of Subjects & Sample Size Calculation:	The sample size selected for this study may be between 20 to 60 treated subjects which are deemed appropriate to assess device safety, per primary safety endpoint of 30 days MAE rate, and with one-sided 95% exact binomial confidence interval to represent the reliability level of the estimated MAE rate and the claim for safety.
Clinical Sites:	Up to 4 recruiting centers, additional sites may be added according to recruitment rate.
Statistical Analysis:	General: Descriptive statistics will be presented per each visit basis. Study Populations: Safety Analysis Set (SA): consist of all subjects enrolled in the study, and underwent the study procedure with the investigational device. The SA set will serve as the main analysis set for safety analyses both primary and secondary. Efficacy Analysis Set (EF): consist of all subjects enrolled in the study, and underwent the study procedure with the investigational device, for which data is available regarding the primary efficacy endpoint and had no major protocol deviations. The EF set will serve as the main analysis set for all efficacy analyses.

Schedule of events:

Visit, Number, (Time point)	Screening Visit 1 (<2m pre-	B-Laser™ procedure Visit 2 (to	Follow up Visit 3 (30d ± 5d	Follow up Visit 4 (6m ± 2w	Follow up Visit 5 (12m ± 1m
	procedure)	discharge)	post procedure)	post procedure)	post procedure)
Informed consent	Х				
Assess eligibility	Х				
Medical history & demographic	X				
Blood Tests	Х				
Con-meds	Х	Х	X	Х	Х
Baseline lesion evaluation	X	X			
Short Physical examination	X				
Ankle-Brachial Index	Х		Х	Х	Х
Rutherford Classification	Х		Х	Х	Х
WIQ	Х		Х	Х	Х
PAD Intervention including B-Laser™ Atherectomy		Х			
Safety- AE, SAE, MAE, ADE		Х	Х	Х	Х

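### Does a safety claim with no stated MAE bound, and a sample size left open between 20 and 60, undermine the primary safety analysis?

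*Combined protocol and SAP*

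**What the plan says.** The synopsis row on number of subjects and sample size reads "The sample size selected for this study may be between 20 to 60 treated subjects which are deemed appropriate to assess device safety". The measure is the 30-day MAE rate, and the tool is a "one-sided 95% exact binomial confidence interval to represent the reliability level of the estimated MAE rate and the claim for safety". The endpoint is listed under Study Endpoints as "30 day Freedom from the following Major Adverse Events (MAE"), with four components.

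The synopsis gives no performance goal, expected MAE rate, power, hypothesis or rule for settling the number treated. The other relevant wording is as follows.

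- Statistical Analysis: "Descriptive statistics will be presented per each visit basis".
- Objective: "To assess the safety and efficacy of the use of" the catheter.
- Study Design: single-arm, and an "open-label, non-randomized clinical study".
- Clinical Sites: up to four, and "additional sites may be added according to recruitment rate".
- Study Duration: "total study expected duration is 15.5 months (3.5 m + 12 m follow-up").

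**The concern.** The sizing sentence gives the interval two jobs: to show how reliable the estimated rate is, and to support a claim. A claim needs a criterion, and none is given. A single-arm study has no control rate to stand in for one. The permitted sample size also spans a factor of three, so the same observed rate can carry quite different upper limits, and calling the whole range appropriate does not show that any one size in it is.

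Because outcomes are open-label, one can imagine the bound, the final number, or both being settled once the MAE count is known. A reader of the synopsis cannot say in advance which count would support the claim. If enrolment were closed because the running count looked favourable, the nominal 95% level could be wrong.

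**Working it through.** **Inputs.** From the synopsis: 20 to 60 treated subjects; one-sided 95% exact binomial interval; 30-day MAE rate. No expected rate or bound is given, so the range of 20 to 60 cannot be reproduced from anything stated. For an adverse event rate the relevant end of the interval is taken to be the upper limit.

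**Step 1: precision across the range.** The exact (Clopper-Pearson) upper limit for x events in N is the 0.95 quantile of a Beta(x + 1, N − x) distribution. For x = 0 it reduces to 1 − 0.05^(1/N).

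- N = 20: 1 − 0.05^(1/20) = 13.9%
- N = 60: 1 − 0.05^(1/60) = 4.9%

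| MAEs | N = 20 | N = 30 | N = 60 |
|---|---|---|---|
| 0 | 13.9% | 9.5% | 4.9% |
| 1 | 21.6% | 14.9% | 7.7% |
| 3 | 34.4% | 23.9% | 12.4% |

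The best attainable limit varies almost threefold (13.9 / 4.9 = 2.8). An observed 5% gives 21.6% as 1/20 and 12.4% as 3/60. The variation is real, but each limit is a correct statement of what its own sample size supports. A small study reports a wide interval, and the reader sees it.

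**Step 2: does a missing bound harm the interval?** For any fixed N in 20 to 60, the chance that the upper limit falls below the true rate is at most 5%, whatever bound is later set beside it. Once x, N and the limit are reported, a reader who prefers a 10% bound and one who prefers 15% can each apply it. A bound chosen late cannot change the limit, and readers need not accept it. The same holds if N is set by recruitment.

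**Step 3: what if N were chosen on the MAE count?** The text neither plans nor excludes this. Its only adaptive phrase concerns adding sites if recruitment calls for it. For size, assume that 60 subjects accrue evenly over 3.5 months (reading the 3.5 months in Study Duration as enrolment) and that outcomes are known at 30 days. Accrual is then 60 / 3.5 = 17.1 a month, so about 17 subjects are unresolved whenever enrolment is stopped. Backward induction over every stopping rule with N from 20 to 60 gives the largest possible non-coverage:

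| True MAE rate | Worst-case non-coverage (nominal 5%) |
|---|---|
| up to about 7.6% | at most 5.0% |
| 10% | 5.8% |
| 15% | 6.2% |
| 20% | 6.0% |
| worst attainable limit between 4% and 40% (just above 10.1%) | 6.5% |

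If every outcome were known at once, the figures at 10%, 15% and 20% would be 7.2%, 10.8% and 10.9%. That extreme does not fit an endpoint that needs 30 days of follow-up.

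**Step 4: which reading fits the text?** The analysis is described as descriptive, the objective is to assess, and there is no hypothesis or power statement. The sizing sentence itself speaks first of the reliability of an estimate. All of this fits estimation with a stated confidence level. Only the closing words about a claim go further.

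**The case for a change.** The strongest reply is that the sentence names the claim in addition to the reliability of the estimate, so the estimation reading leaves some of its words unexplained. With open-label MAEs in view, a sponsor could pick a bound that the result happens to meet and call the claim supported. Some bounds could not be met at all at the low end of the range. Against an illustrative 10% (an assumption, not in the documents), 0/28 gives 10.15% and fails, while 0/29 gives 9.81% and passes. Slower accrual, or MAEs seen well before day 30, would also move the non-coverage in Step 3 towards the no-delay figures.

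Part of this stands. The synopsis states no criterion, and a later statement that the claim was met would have no confirmatory standing beyond the reported count and limit. But the consequence is confined to how a sentence in a report is phrased. The count, rate and limit are the same with or without a bound, so a convenient bound is visible as such. The coverage argument needs a stopping practice that the text does not describe and, in the worst case, a rule built to exploit it. The failure of small samples against 10% depends on a bound that nobody has proposed.

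**Conclusion.** No change to the plan follows. The observation is accurate: the synopsis mentions a safety claim without a criterion, gives no rule for the final number, and allows the zero-event upper limit to range from 13.9% to 4.9%. It is a gap that analysts fill sensibly, by reporting the MAE count, the number treated and the exact upper limit in the Safety Analysis Set, and by reading the result as an estimate.

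Stating a bound, or dropping the loose phrase about a claim, would leave that estimate and interval unchanged. A number of subjects determined by recruitment within a range is also compatible with an exact limit.

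This rests on N being fixed or set by recruitment, which is the natural reading because no MAE-based stopping is described. If that failed, non-coverage would be at most about 6.5% against 5% under the assumed accrual and 30-day delay, with no inflation at true rates up to about 7.6%. The conclusion concerns only the three-page synopsis; a fuller protocol or a separate SAP may state a criterion.

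### Efficacy is analysed mainly in a set that drops treated subjects for major protocol deviations or a missing crossing result, with no all-treated efficacy analysis stated, so the technical-success rate can be biased, mostly upward when success is high

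*Combined protocol and SAP*

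**What the plan says.** All references are to the combined protocol and SAP, which is a three-page synopsis.

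- **Statistical Analysis, Study Populations.** The all-treated set is "Safety Analysis Set (SA): consist of all subjects enrolled in the study, and underwent the study procedure with the investigational device". Its assigned use is safety: "The SA set will serve as the main analysis set for safety analyses both primary and secondary". EF starts from the same subjects and keeps only those "for which data is available regarding the primary efficacy endpoint and had no major protocol deviations". Its use is broad: "The EF set will serve as the main analysis set for all efficacy analyses".
- **Study Design.** "Prospective, single-arm, multi-center, international, open-label, non-randomized clinical study".
- **Primary Endpoint, Effectiveness.** "Ability of the B-Laser™ to cross the target lesion stenosis over the wire". The sentence goes on to add a condition: the open lumen at the stenosis must be narrower than the catheter.
- **Secondary Endpoints, Effectiveness.** Residual stenosis after adjunctive therapy, restricted to cases where such therapy is medically appropriate, and improvement in ABI, Rutherford class and WIQ at 30 days, 6 months and 12 months.
- **Number of Subjects.** 20 to 60 treated subjects, justified by the 30-day MAE rate only.

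The synopsis does not define a major deviation. It does not say who classifies deviations or when, gives no rule for a missing crossing result, and names no supportive efficacy analysis in SA.

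**The concern.** Both EF filters act on subjects who have already been treated. Technical success is seen on the table by an unblinded operator, so whether a deviation counts as major can be settled by people who know whether the catheter crossed. Several eligibility rules concern how difficult the lesion or vessel is (lesion length, vessel size relative to the catheter, wire position in the true lumen). A deviation from one of them may therefore be related to the crossing result. If failures and successes are excluded at different rates, the EF rate departs from the rate among everyone treated. With no control arm to share the selection, the departure passes straight into the reported figure.

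There is a second effect. Because EF governs all efficacy analyses, a subject without a crossing result also leaves the ABI, Rutherford and WIQ analyses, even if those were measured at every visit. No reason is given for tying them to the crossing result.

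At stake is the credibility of the primary effectiveness estimate. The synopsis sets no performance goal for technical success, so no pass/fail decision is at risk.

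**Working it through.** **Inputs.** From the documents: 20 to 60 treated subjects, a single arm and the two EF filters. Not in the documents: the success rate, the exclusion rate and the share of missing results. The counts below are assumed, with one crossing result per subject. There is no planned figure for technical success to reproduce, and the sample-size range comes without an expected rate, a performance goal or a precision target.

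**Step 1. Range of the EF rate.** With n treated, x crossed and k excluded, the EF rate runs from (x − k)/(n − k), if every excluded subject was a success, to x/(n − k), if every one was a failure (k ≤ n − x).

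| Treated, crossed | All-treated rate | Excluded | Only successes removed | Only failures removed | Shift in points |
|---|---|---|---|---|---|
| 20, 18 | 90.0% | 1 | 17/19 = 89.5% | 18/19 = 94.7% | −0.5 to +4.7 |
| 20, 18 | 90.0% | 2 | 16/18 = 88.9% | 18/18 = 100% | −1.1 to +10.0 |
| 60, 54 | 90.0% | 1 | 53/59 = 89.8% | 54/59 = 91.5% | −0.2 to +1.5 |
| 60, 54 | 90.0% | 3 | 51/57 = 89.5% | 54/57 = 94.7% | −0.5 to +4.7 |

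**Step 2. Why the range is lopsided.** Subtracting x/n from each end gives a largest rise of [k/(n − k)] × (x/n) and a largest fall of [k/(n − k)] × (1 − x/n). Their ratio is x/(n − x), which is 9 to 1 at 90% success.

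**Step 3. Reading back from a reported EF rate.** With s successes in EF, the all-treated rate lies between s/n and (s + k)/n. If 2 of 20 are excluded and EF shows 17/18 = 94.4%, the all-treated rate is between 17/20 = 85.0% and 19/20 = 95.0%. If 6 of 60 are excluded and EF shows 52/54 = 96.3%, it is between 52/60 = 86.7% and 58/60 = 96.7%.

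**Step 4. Expected bias.** With true rate p, and shares f of failures and s of successes excluded, the expected EF rate is approximately p(1 − s)/[p(1 − s) + (1 − p)(1 − f)]. For p = 0.90:
- f = 0.20, s = 0.02: 0.882/(0.882 + 0.080) = 91.7%.
- f = 0.02, s = 0.20: 0.720/(0.720 + 0.098) = 88.0%.
- f = s: 90.0%, so there is no bias.

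**Step 5. Missing crossing result.** An observed failure is endpoint data, so the data-available filter does not remove it; that filter acts only on results that are truly missing. With 20 treated, 17 crossed, 2 failed and 1 missing, EF gives 17/19 = 89.5%. Counting the missing result as failure and then as success gives 17/20 = 85.0% to 18/20 = 90.0%.

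**Step 6. The right denominator.** The endpoint applies only where the residual lumen is narrower than the catheter. Eligibility requires at least 70% stenosis and a reference lumen of at least 150% of the catheter diameter, with no upper limit. If percent stenosis means diameter stenosis (an assumption), a 70% stenosis leaves 30% of the reference lumen. The residual lumen then reaches the catheter diameter once the reference lumen is 1/0.30 ≈ 3.3 catheter diameters. So SA may include subjects for whom passing the lesion does not meet the endpoint, and an all-treated analysis must say how they count.

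**The case against.** The strongest reply has four parts.

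- **The EF rule is written in advance and can serve a purpose.** Both are true. A treated subject whose stenosis turns out to be below 70% may be an easy crossing, and excluding that subject removes a favourable result. The all-treated rate could therefore be higher than the EF rate. This supports showing both sets. It does not support having only the filtered set, because membership still depends on classifications that may be made after the result is known.
- **This is a synopsis.** A fuller plan may define major deviations and add supportive analyses, and calling EF the main set leaves room for them. The silence is established only for the supplied text. But the assignment of EF to all efficacy analyses is a stated rule, not an omitted detail.
- **The size is assumed and modest beside sampling error.** This stands. The exact one-sided 95% lower limit is 71.7% for 18/20 and 81.2% for 54/60, which is 18.3 and 8.8 points below the estimate. The expected shifts in Step 4 are +1.7 and −2.0 points and need a tenfold difference in exclusion shares. The 18/18 case needs every failure to be excluded. Unlike sampling error, however, a selection effect is not shown by a confidence interval.
- **Unrestricted SA does not fit the endpoint.** This also stands, because of the diameter condition, and the fix allows for it.

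A reader might go further and infer that EF discards failed crossings as missing data, or that a missed late follow-up visit would remove a subject. The text supports neither. A failed crossing is an available result, and nothing classes a missed visit window as a major deviation.

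**Conclusion.** The concern holds in a limited form. As written, the main efficacy set can exclude treated subjects after the crossing result is known, and the supplied synopsis names no all-treated efficacy result to set beside it. Under the assumed 90% success, one exclusion moves the rate by −0.5 to +4.7 points at 20 subjects and by −0.2 to +1.5 at 60. The practical risk at high success is overstatement. The actual size cannot be known, because the documents give neither a success rate nor an exclusion rate, and exclusions unrelated to crossing would cause no bias. The loss of measured ABI, Rutherford and WIQ values when the crossing result is missing follows directly from the EF definition and needs no assumed rate, although such subjects may be few.

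A reader might infer that the reported rate will be inflated, or that a success claim could be reversed. The documents support neither: they do not show that failures will be excluded preferentially, and they set no threshold to pass. This is an inexpensive improvement to the primary effectiveness estimate, not a defect that invalidates the study.

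**What to change.** 1. Report technical success as the main result in all SA subjects whose lumen at the stenosis, before crossing, is narrower than the catheter, as the endpoint requires. Remove no one for protocol deviations. Count attempted but failed or aborted crossings as failures. Show truly missing results once as failure and once as success. Give the number of treated subjects outside the diameter condition, and add a rate in all of SA that counts them as not meeting the endpoint.
2. Keep EF as a sensitivity analysis. Classify major deviations without reference to the crossing result, and list each exclusion with its reason.
3. Analyse ABI, Rutherford and WIQ in all treated subjects with data at the visit, whether or not a crossing result exists. Show the number with data out of all treated.
4. Draw the residual-stenosis analysis from SA, limited to the cases its own definition covers (adjunctive therapy medically appropriate).

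**Cost.** A few lines of text and a few tables, with no new subjects or data. The reported rate may become slightly lower, or higher if the excluded subjects were mostly successes.
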